## 5.12. Health Outcomes/Quality-of-Life Analyses

The description and derivation of the health outcomes/QoL analyses are described in Table KGBO.5.4. For categorical parameters, the number and percentage of patients in each category will be presented, as well as a 90% Wilson-Score confidence interval for the percentage. For continuous parameters, descriptive statistics will include n (number of patients), mean, standard deviation, Q1, median, Q3, minimum, and maximum. These summaries will be provided for the data as-observed and after implementation of LOCF and MCMC-MI imputation as described in Sections 5.4.2. and 5.4.3. Patient-Reported Outcomes Information System and DLQI/CDLQI will be reported by clinic visit.

## 5.13. Safety Analyses

The planned analyses of safety data will be performed with an intent to maintain consistency with compound-level standard safety analyses. These standards are based on internal standards which were informed by CDISC standards, regulatory guidance (eg, FDA Clinical Review Template), and cross-industry standardization efforts (eg, PhUSE white papers from the Standard Analyses and Code Sharing Working Group provided in the PhUSE Computational Science Deliverables Catalog [WWW]).

The laboratory (including hormone), vital sign (including growth), and immunogenicity safety summaries will be based on the safety population. The extent of exposure and AE tables will be based on the safety population.

These analysis populations are fully defined in Table KGBO.5.1.

Not all displays described in this section will necessarily be included in the CSRs. Any display described and not provided in the CSR would be available upon request. Not all displays will necessarily be created as a "static" display. Some may be incorporated into interactive display tools instead of or in addition to a static display. Any display created interactively will be included in the CSR if deemed relevant to the discussion.

### 5.13.1. Extent of Exposure

A by-patient listing of exposure duration with the number of active injections and total dose will be provided for the Safety Population.

The duration of exposure will be calculated as:

```
Duration of exposure (days) =
Date of last visit (scheduled or unscheduled) in the Treatment Period –
Date of first dose+1
```

The number and percentage of patients in each of the following categories will be included in the summaries:

Page 42

>0,  $\geq$ 7 days,  $\geq$ 14 days,  $\geq$ 30 days,  $\geq$ 60 days,  $\geq$ 90 days,  $\geq$ 112 days,  $\geq$ 120 days,  $\geq$ =168 days. Note that patients may be included in more than 1 category.

The summaries will also include the following information:

• total exposure in patient years, calculated as:

```
Total exposure in patient years
```

```
= \frac{Sum of duration of exposures for all patients in treatment group}{365.25}
```

- mean and median total dose; total dose (in mg) is calculated by the number of active injections taken multiplied by 250.
- Total number of injections received will be derived from the *Exposure as Collected* eCRF page and on the *Exposure as Collected: Missed Injections at Home* eCRF page.

## 5.13.2. Adverse Events

A TEAE is defined as an event that first occurred or worsened in severity after baseline (ie, AEs with an onset date on or after the date of the first injection of study drug). The MedDRA lowest-level term will be used in the treatment-emergent computation. The maximum severity for each lowest-level term during the baseline period will be used as baseline. The treatment period will be included as post-baseline for the summaries. For events with a missing severity during the baseline period, the events will be treated as 'mild' in severity for determining treatment-emergence. Events with a missing severity during the postbaseline period will be treated as 'severe', and treatment-emergence will be determined by comparing to baseline severity. For events occurring on the day of first taking study medication, the events will be assumed to be posttreatment.

The planned summaries for AEs are provided in Table KGBO.5.5 and are described more fully in compound-level safety standards and in the AE-related PhUSE white paper [Analysis and Displays Associated with Adverse Events: Focus on Adverse Events in Phase 2-4 Clinical Trials and Integrated Summary Document (PhUSE 2017)].

Summary tables will be presented for the safety population. Summary tables will include the number and percentage of patients reporting an event. For events that are gender-specific (as defined by MedDRA), the number of participants at risk will include only patients from the given gender.

Summaries	Population
Overview of AEs	Safety
Summary of TEAEs by PTs	Safety
Summary of TEAEs by PTs within SOC	Safety
Summary of TEAE PTs by maximum severity	Safety
Summary of SAEs by PT within SOC	Safety
Summary of AEs leading to treatment discontinuation by PT with SOC	Safety

Table KGBO.5.5.Summary Tables/Listings Related to Adverse Events

Summary of TEAEs possibly related to study drug by PTs within SOC	Safety
Summary of treatment-emergent adverse events – facial dermatitis follow-up form	Safety
Listing of SAEs (including Death)	Safety
Listing of primary AEs leading to study treatment discontinuation	Safety
Listing of TEAEs	Safety

Abbreviations: AE = adverse event; PT = Preferred Term; SAE = serious adverse event; SOC = System Organ Class; TEAE = treatment-emergent adverse event.

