6.7. Treatment of Overdose

For this study, any dose of lebrikizumab greater than 500 mg (baseline and Week 2) and 250 mg Q2W (Week 4 and beyond) will be considered an overdose.

Sponsor does not recommend specific treatment for an overdose.

In the event of an overdose, the investigator/treating physician should:

- Contact the medical monitor immediately.
- Evaluate the participant to determine, in consultation with the medical monitor, whether study intervention should be interrupted or whether the dose should be reduced.
- Closely monitor the participant for any AE/SAE and laboratory abnormalities until lebrikizumab can no longer be detected systemically (at least 18 weeks).

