8.3.1. Timing and Mechanism for Collecting Events

This table describes the timing, deadlines, and mechanism for collecting events.

Event	Collection Start	Collection Stop	Timing for Reporting to Sponsor or Designee	Mechanism for Reporting	Back-up Method of Reporting
Adverse Event					
AE	Signing of the ICF	Participation in study has ended	As soon as possible upon site awareness	AE CRF	N/A
Serious Adverse Event					
SAE and SAE updates – prior to start of study intervention and deemed reasonably possibly related to study procedures	Signing of the ICF	Start of intervention	Within 24 hours of awareness	SAE paper form	SAE paper form
SAE and SAE updates – after start of study intervention	Start of intervention	Participation in study has ended	Within 24 hours of awareness	SAE paper form	SAE paper form
SAE ^a – after participant’s study participation has ended and the investigator becomes aware	After participant’s study participation has ended	N/A	Promptly	SAE paper form	N/A
Pregnancy					
Pregnancy in female participants and female partners of male participants	After the start of study intervention	At least 18 weeks after the last dose of study intervention	Within 24 hours (see Section 8.3.2)	Pregnancy paper form	Pregnancy paper form

Event	Collection Start	Collection Stop	Timing for Reporting to Sponsor or Designee	Mechanism for Reporting	Back-up Method of Reporting
Product Complaints					
PC associated with an SAE or might have led to an SAE	Start of study intervention	End of study intervention	Within 24 hours of awareness	PC form	N/A
PC not associated with an SAE	Start of study intervention	End of study intervention	Within 1 business day of awareness	PC form	N/A
Updated PC information	—	—	As soon as possible upon site awareness	Originally completed PC form with all changes signed and dated by the investigator	N/A
PC, if investigator becomes aware	Participation in study has ended	N/A	Promptly	PC form	

Abbreviations: AE = adverse event; ICF = informed consent form; N/A = not applicable; PC = product complaint
SAE = serious adverse event.

^a Serious adverse event should not be reported unless the investigator deems them to be possibly related to study treatment or study participation.

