9.3.5. Safety Analyses

All safety data will be descriptively summarized using the safety population.

Treatment-emergent AEs are defined as AEs that first occurred or worsened in severity after the first dose of study treatment. The number of TEAEs as well as the number and percentage of participants who experienced at least 1 TEAE will be summarized using MedDRA (Medical Dictionary for Regulatory Activities) for each system organ class (or a body system) and each preferred term. SAEs and AEs that lead to discontinuation of study intervention will also be summarized.

All clinical laboratory results will be descriptively summarized. Individual results that are outside of normal reference ranges will be flagged in data listings. Quantitative clinical hematology, chemistry, and urinalysis variables obtained at the baseline to postbaseline visits will be summarized as changes from baseline. Categorical variables, including the incidence of abnormal values and incidence of AEs of special interest, will be summarized by frequency and percentage of participants in corresponding categories. Shift tables might be presented for selected measures.

Observed values and changes from baseline (predose or screening if missing) for vital signs and physical characteristics will be descriptively summarized by time point.

The SAP may include additional safety analyses if needed.

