#### **Study Periods**

This trial has 4 study periods:

- Screening (Visit 1:  $\leq$ 30 days prior to baseline)
- Treatment (Visits 2-9: 24 weeks)
- Safety follow-up (Visit 801: at Week 34 or approximately 12 weeks after last treatment)
- Continued Access (Visits 501, 502, and 503)

Participants who enroll into KGBO Protocol Addendum 2 will move directly into the Continued Access Period after completing the 24-week treatment period. Such participants will not complete Visit 801. A post-treatment follow-up visit (V901) will occur approximately 12 weeks post the last dose at the end of the Continued Access Period for the participants who do not move to commercial lebrikizumab or who discontinued early from the Continued Access Period. Please refer to KGBO Protocol Addendum 2 for more information.

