# 5.13.2.2. Deaths, Other Serious Adverse Events and Other Notable Adverse Events

The number and percentage of patients reported with an SAE during the treatment period will be summarized using MedDRA PT. A listing of SAEs will be provided.

The number and percentage of patients who permanently discontinued from study treatment due to an AE (including AEs that led to death) during the treatment period will be summarized using MedDRA PT. Events will be ordered by decreasing frequency.

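### The SAP names only the treatment period as post-baseline for its AE summaries, so TEAEs and SAEs with onset in safety follow-up fall outside the CSR incidence tables as written

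*SAP*

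**What the plan says.** SAP 5.13.2 states: "The treatment period will be included as post-baseline for the summaries". It names no other period. SAP 5.13.2.2 is more explicit for serious events: "The number and percentage of patients reported with an SAE during the treatment period will be summarized using MedDRA PT". The same subsection says that permanent discontinuations of study treatment "due to an AE (including AEs that led to death) during the treatment period will be summarized using" preferred terms.

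The SAP's list of study periods (Section 4.1) shows what the treatment period is. One entry reads "Treatment (Visits 2-9: 24 weeks". A separate entry reads "Safety follow-up (Visit 801: at Week 34 or approximately 12 weeks after last treatment". So follow-up is not part of the treatment period in the SAP's own terms.

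Other parts of the plan point the other way:
- Protocol 9.3.5 sets no end to treatment emergence: "Treatment-emergent AEs are defined as AEs that first occurred or worsened in severity after the first dose of study treatment". The SAP's own definition in 5.13.2 also starts at the first injection and has no end.
- Protocol 8.3.1 stops collection of AEs and of post-dose SAEs at "Participation in study has ended", and the Schedule of Activities marks AE collection at Visit 801.
- Protocol 8.2 gives safety assessment as the purpose of follow-up, and the final database lock in SAP 5.16 waits for follow-up to finish.

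**The concern.** Safety is a stated aim of this study. The plan collects adverse events for about 12 weeks after the last dose and holds the final lock until they are in. It then names a window for the CSR summaries that does not reach them.

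What is at stake is mainly the non-serious events of special interest, such as conjunctivitis and herpes infections. The SAP reports these as TEAE summaries, so they take whatever TEAE window is programmed. There is also a risk of inconsistent output. One programmer applying the open-ended TEAE definition and another applying the post-baseline sentence could produce different tables from the same data. A single follow-up SAE would make the CSR count under 5.13.2.2 differ from the registry count under 5.18, although 5.18 says AE reporting agrees with the CSR.

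**Working it through.** **Inputs (nominal weeks)**
- Last dose: Week 22 for inadequate responders (Q2W), Week 20 for responders (Q4W); SAP 4.1, Dosing.
- Visit 801: about 12 weeks after the last dose.
- End of the treatment period for completers: Week 24 (Visit 9).
- Screening: up to 30 days.
- Planned enrolment: 120.

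**Reproducing the plan's own figures**
- Visit 801, Q2W: 22 + 12 = Week 34, which matches the SAP.
- Visit 801, Q4W: 20 + 12 = Week 32.
- Longest participation: 30/7 + 22 + 12 = 38.3 weeks, against the stated maximum of 38.

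**Follow-up time outside the treatment period, per completer without Continued Access**

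The 12 weeks run from the last dose, so the first 2 (Q2W) or 4 (Q4W) of them fall inside the treatment period.
- Q2W: 34 − 24 = 10 weeks; 10/34 = 29.4% of observation after the first dose.
- Q4W: 32 − 24 = 8 weeks; 8/32 = 25.0%.

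**Study-wide share, assuming all 120 complete and half are responders**
- Treatment period: 120 × 24 = 2880 person-weeks; × 7/365.25 = 55.2 patient-years.
- Follow-up with no Continued Access: 120 × (0.5 × 8 + 0.5 × 10) = 1080 person-weeks = 20.7 patient-years; 1080/(1080 + 2880) = 27.3%.
- With no Continued Access, the range from 100% to 0% responders is 18.4 to 23.0 patient-years (25.0% to 29.4%).

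Participants who enter Continued Access skip Visit 801. The documents give no expected uptake, so a range is shown, with half responders:

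| Assumed uptake | Follow-up person-weeks | Share omitted |
|---|---|---|
| 0% | 1080 | 27.3% |
| 25% | 810 | 22.0% |
| 50% | 540 | 15.8% |
| 75% | 270 | 8.6% |

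**Early discontinuers**

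The SAP does not say when the treatment period ends for them. Take a last dose at Week 4, with follow-up to Week 16. If the period ends at the last dose, 12/16 = 75% of observed time is outside it. If it is 24 calendar weeks, nothing is outside. The documents do not settle which applies.

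**Where a follow-up event would appear**
- An SAE: in the SAE listing, which states no period limit, and in the SAP 5.18 registry summary, which counts SAEs whether or not they are treatment-emergent. It is outside the count in 5.13.2.2.
- A non-serious event: the registry category for other AEs requires a TEAE, so it carries the same uncertainty as the CSR tables, and so does the TEAE listing. No summary clearly includes it.

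**Is the limit deliberate?** SAP 5.13.1 ends exposure at the last treatment-period visit. SAP Table KGBO.5.8 counts liver test elevations in the treatment period, although chemistry is also drawn at Visit 801. The same boundary is used repeatedly, which makes a slip of wording less likely.

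**The case against.** The strongest reply is that this is ambiguity rather than exclusion. The sentence in 5.13.2 does not say that only the treatment period counts, and the TEAE definition beside it is open-ended. The SAE row of Table KGBO.5.5 and the infection and conjunctivitis tables state no period. The protocol's glossary (Appendix 11) ties a TEAE to a defined treatment period, so such a window has some protocol support. It also matches the exposure calculation in 5.13.1. Pooling follow-up events would mix unequal observation times, because Continued Access entrants have no Visit 801. The SAP refers to compound-level safety standards for fuller detail; these are not among the documents and may specify follow-up displays.

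Much of this stands. A reader might infer that follow-up events are missing from every incidence table. The documents do not support that, because the registry summary in SAP 5.18 gives participants at risk and participants affected, and counts SAEs with no period limit. Nor is this a simple departure from the protocol, given the glossary. A reader might also infer that participants who stop because of an AE lose the most. That rests on an unstated end of their treatment period, and the AE that led to stopping is normally an on-treatment event and so counted. Protocol 6.7 asks for monitoring after an overdose "until lebrikizumab can no longer be detected systemically (at least 18 weeks"; this makes residual drug during follow-up plausible but does not describe exposure after the scheduled regimen.

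What does not fall away is the explicit limit on SAEs in 5.13.2.2, and the fact that the only period named as post-baseline excludes Visit 801. The pooling objection is a reason to report follow-up separately, not to leave it unreported.

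**Conclusion.** The point holds for the CSR TEAE and SAE incidence summaries. Followed as written, they leave out events that start after the treatment period, and the text conflicts with the SAP's own open-ended TEAE definition. The omitted time is 25% (Q4W) or 29% (Q2W) of post-first-dose observation for a completer who does not enter Continued Access. Study-wide it is 27% with no uptake and about 16% at 50% uptake, assuming full completion and half responders. These figures describe observation time; the documents give no basis for saying how many events would be missed. No firm figure can be given for early discontinuers. The conclusion is subject to the compound-level standards, which could add follow-up displays but would still leave the SAP's sentences to be reconciled. The change should be made, because it affects what the safety report shows and uses data already collected.

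**What to change.** In SAP 5.13.2 and 5.13.2.2:

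1. Keep the treatment-period column. Add a separate follow-up column or table for TEAEs, SAEs and AESIs with onset after the treatment period through Visit 801. Use the number of participants who entered follow-up as the denominator.
2. State when the treatment period ends for participants who discontinue early.
3. Reconcile the TEAE definition with the post-baseline sentence, and the CSR SAE count with the registry count in SAP 5.18.

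The AE-discontinuation table needs no extension, because study treatment has already stopped by follow-up.

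The cost is a few sentences of SAP text and one extra column or table to program. No new data are needed, and the treatment-period figures stay as a separate column.

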#### 5.13.2.1. Common Adverse Events

The percentages of patients with TEAEs will be summarized using MedDRA PT for the common TEAEs (occurred in  $\geq 1\%$  before rounding in any column in the table).

# 5.13.2.2. Deaths, Other Serious Adverse Events and Other Notable Adverse Events

The number and percentage of patients reported with an SAE during the treatment period will be summarized using MedDRA PT. A listing of SAEs will be provided.

The number and percentage of patients who permanently discontinued from study treatment due to an AE (including AEs that led to death) during the treatment period will be summarized using MedDRA PT. Events will be ordered by decreasing frequency.

## 5.13.3. Clinical Laboratory Evaluation

As described more fully in compound-level safety standards and in the laboratory-related PhUSE white papers (PhUSE 2013; PhUSE 2015), the clinical laboratory evaluations will be summarized as described in Table KGBO.5.6. Hormone analytes are summarized/plotted similarly.

Summaries	Population
Box plots of observed values by visit	Safety
Box plots for change from baseline values by visit	
Change from baseline to last observations	Safety
Treatment-emergent abnormal high lab values (ie, patients shifting from a normal/low maximum baseline value to a high maximum postbaseline value) or abnormal low lab values (ie, patients shifting from normal/high minimum baseline value to a low minimum postbaseline value)	Safety
Shift tables showing the number of patients who shift from each category of maximum (minimum) baseline observation to each category of maximum (minimum) postbaseline observation. Here categories may be low, normal, or high with cut-offs defined in the compound-level safety standards.	Safety
Listing of abnormal findings for laboratory analyte measurements, including qualitative measures	Safety

Table KGBO.5.6.Summary Tables/Listing of Clinical Laboratory Evaluations

## 5.13.4. Vital Signs and Other Physical Findings

As described more fully in compound-level safety standards and in the laboratory-related PhUSE white papers (PhUSE 2013; PhUSE 2015), vital signs will be summarized similarly to the clinical laboratory evaluation (Table KGBO.5.7). For vital signs, treatment-emergent low and high are based on a combination of a specified value and a change or percentage change as defined in the compound-level safety standards.

Table KGBO.5.7.	Summary	Tables/Figures	Related to	Vital Signs
	Gammary	Tubico/Tiguico	itolatoa to	Vital Olgilo

Summaries	Population
Box plots for observed values by visit	Safety
Box plots for change from baseline values by visit	Safety
Tables with the number and percentage of subjects who shift from normal/high to low (ie, treatment-emergent low) and the number and percentage of subjects who shift from normal/low to high (ie, treatment-emergent high); the limits are defined in the compound-level safety standards	Safety

## 5.13.5. Immunogenicity

Anti-drug antibodies (ADA) analysis will only occur upon request from, for example, regulatory or a business need. An individual sample will be potentially examined multiple times in a hierarchical procedure to produce a sample ADAs assay result and may yield a sample NAb assay result. Treatment-emergent ADAs are defined as those with a titer 2-fold (1 dilution) greater than the minimum required dilution if no ADAs were detected at baseline (treatment-induced ADA) or those with a 4-fold (2 dilutions) increase in titer compared to baseline if ADAs were detected at baseline (treatment-boosted ADA). A patient is considered TE-ADA positive when at least 1 postbaseline ADA sample meets the definition of TE-ADA.

Compound-level safety standards will be followed in the analyses of immunogenicity. Listings of immunogenicity assessments will be provided along with the summary of specified TEAEs by

TE-ADA status. The summary of TE-ADA and NAb status will be produced for the Safety Population.

## 5.13.6. Special Safety Topics including Adverse Events of Special Interest

This section includes areas of interest whether due to observed safety findings, potential findings based on drug class, or safety topics anticipated to be requested by a regulatory agency for any reason. In general, potential AESI relevant to these special safety topics will be identified by 1 or more SMQs, by a Lilly-defined MedDRA PT listing based upon the review of the most current version of MedDRA, or by treatment-emergent relevant laboratory changes, as described below. Additional special safety topics may be added as warranted.

Unless otherwise specified, the AESI will be summarized for the safety population.

Full details of the search terms and rules for deriving AESI in each of the sections below are described in the compound-level safety standards along with information about the types of summaries and listings to be provided. In the event that the listing of terms or analysis changes for a special safety topic, it will be documented in the compound-level safety standards, which will supersede this document; it will not warrant an amendment to the individual study SAP.

